### 3.2.2. Non-Specific Low Back Pain

As stated earlier, almost 90% of all LBP incidents are of non-specific origin, meaning none of the “red flags” were present and no imaging results showed any diseases. The combination of both indicators is important, as plain radiographs are not sensitive enough

as well as not specific enough [Tul97]. In other words: imaging results are not associated distinctively with symptoms and the origin of symptoms cannot be found with imaging alone. Since there are no precise pathoanatomical diagnosis terms such as strain, sprain, sacroiliac syndromes, facet joint syndrome or lumbago are most commonly used to describe non-specific LBP [AD01, DW01].

In order to better understand this difficult to define and very difficult to diagnose of LBP it is important to look at recent advances in the field of biomechanics.

### 3.3. Clinical Spinal Instability

Literature suggests that spinal instability is an important cause of LBP and disability as well as increasing the risk of recurrence [Izz13, Dem07].

A commonly used definition for instability as proposed by Panjabi is: “A significant decrease in the capacity of the stabilizing system of the spine to maintain the intervertebral neutral zones within the physiological limits so that there is no neurological dysfunction, no major deformity, and no incapacitating pain” [Pan92]. Understanding this definition requires deeper insight in the terms of the “stabilizing system” and the “neutral zones”.

The spinal stabilizing system (Figure 2) consists of three subsystems: a neural or motor control unit, muscles surrounding the spine, and the spinal column itself. Loads are carried by the spinal column and information about the position, motion and quantity of load is sent to the neural control unit. The neural control unit in turn transforms information into action, which is carried out by the muscles.

Normally all of these subsystems work in harmony and by doing so provide the necessary mechanical stability of the spine [Pan03].

[figure not shown]

Figure 2: The Spinal Stabilizing System [Pan03]

The neutral zone Panjabi described is the “part of the range of intervertebral motion, measured from the neutral position, in which spinal motion can occur with minimal non-muscular passive resistance from the spine” [FWW10].

Abnormal motion would coincide with an increase of the neutral zone. This would force the stabilizing system to react by stiffening muscles surrounding the spine, and actively decrease the neutral zone again. Panjabi used a ball-in-a-bowl analogy to illustrate this. In a healthy subject, the ball can move freely within the neutral zone (Figure 3 A). After sustaining an injury or degenerative changes, the ball is able to move beyond the neutral – and therefore pain free-zone (Figure 3 B). After the adaptation of muscles (Figure 3 C), the neutral zone is decreased again and the subject is pain free. This analogy leads to a very important aspect of stabilization and therefore possible cause of LBP – muscles.

[figure not shown]

Figure 3: Ball-in-a-Bowl Analogy [Pan03]

### 3.3.1. Muscles

Panjabi postulated that in-vitro critical load calculations for the lumbar spinal column alone were around 90N, which is a lot less than the estimated in-vivo loads of 1500N. This would suggest that only through the stiffening effect of the muscles, the increased load and stability of the spine is even possible [Pan03]. Examining literature especially the transversus abdominis muscles and the lumbar multifidus muscles seem to play an important role [FWW10, Hid11, Won14, Sal10] in LBP origin and treatment. Studies have also shown a muscular imbalance in patients with LBP [Won14]. Muscular imbalance refers to differences in size and strength of muscles in the left to right relation, in case of the lumbar spine. The local stabilizing muscles are especially negatively affected by this pathophysiological mechanism. Ultrasound investigations have shown that the local stabilizing muscles of the lower back have a reduced thickness and increased fatty deposits on the side and level where the LBP is located. Even after an episode of LBP has resolved, the reduced muscle mass and the fatty deposits stay present. This observation is one of the key concepts which explain the high recurrence rates of LBP. Reduced local stability of the stabilizing muscles of the lower back exposes those effected by LBP to a higher risk of traumatizing the surrounding structures of the lumbar spine during motions of everyday life. Hence, recurrent episodes of LBP are like to occur, until the problem of localized muscle mass reduction is going to be addressed.

### 3.3.2. Lumbar Multifidus Muscles

According to Wilke et al. [WWC+95]. M. Multifidus make up two thirds of overall spinal stability, therefore being the largest stability contributing factor. The multifidus is made up of several fascicles that rise from the processus spinosus and lamina of each vertebra and insert in caudal direction between two and five spinal levels onto the zygapophyseal joint capsule, mammillary process, lamina, medial posterior superior iliac spina, as well as dorsal sacrum [Dem07, MMH06]. Compared to all other lumbar muscles, the lumbar multifidus has characteristic short and strong muscle fibers with a high cross-sectional area due to a high mass. This in turn allows dense arrays of muscle fibers and makes the lumbar multifidus ideal for stability purposes [FWW10, RRA08].

The lumbar multifidus can be categorized in deep fibres (DM) and superficial fibres (SM) and are part of the erector spinae muscle (ES). DM are defined as crossing only two and not five spinal levels and then inserting onto the lamina, mammillary process and zygapophyseal joint capsule [Mac86]. The sacrospinal ES consists of two independent muscles, the iliocostalis lumborum and the longissimus thoracis, each with thoracic and lumbar parts, the lumbar parts being here of relevance. The lumbar parts rise from the accessory process as well as the L1-4 transverse processes and then insert in the ilium [MB87]. MacDonald et al. identified five common beliefs concerning DM, SM and ES [MMH06]:

- (1) SM and ES function as rotators/extensors of the lumbar spine and do not stabilize like the DM;
- (2) SM and ES are to a lesser extent made up of type I (slow twitch) muscle fibers compared to DM;
- (3) SM and ES are active phasically, DM tonically during trunk movement and gait;
- (4) Transversus abdominis and DM co-contract;
- (5) Lumbar paraspinal muscles changes in combination with LBP has a greater effect on DM than SM or ES.

Bridging exercises, which also will be used during the pilot 2 with the ALFRED Back Trainer, were able to activate to lumbar multifidus to a high degree, especially if combined with active motions of the extremities.

### 3.3.3. Transversus Abdominis Muscles

It has been suggested that elevated intra-abdominal pressure and contraction of the thoracic diaphragm and transversus abdominis provide a mechanical contribution to the control of spinal intervertebral stiffness [Hod03]. Additionally, the ability to contract the lumbar multifidus muscles, which as mentioned play a large role in non-specific LBP, has been suggested to be related to the ability to contract the transversus abdominis [Hid11]. It is only logical then that transversus abdominis muscle dysfunction is associated with higher long-term incidence rates of LBP as well [Mos04].

The transverse abdominis muscles connect to the lumbar vertebrae through the thoracolumbar fascia, which forms a corset resembling structure around the trunk that controls intra-abdominal pressure as well as vertebral stiffness [Won13]. The exact role of intra-abdominal pressure remains unclear, but it plays a role in stabilizing the spine and reducing spinal loading [AS06] which has also been observed in experimental studies [Hod03].

D8 3 1 Piloting Validation II Hospital.docx	Document Version: 1.0	Date: 2016-03-31	Status: For Approval	Page: 18 / 34
http://www.alfred.eu/		Copyright © ALFRED Project Consortium. All Rights Reserved. Grant Agreement No.: 611218		

Subsequently there have been several assumptions regarding the role of transversus abdominis [Led10]:

- (1) certain muscles are more important for the stabilization of the spine than others (such as transversus abdominis),
- (2) weak abdominal muscles lead to back pain,
- (3) strengthening abdominal or trunk muscles may reduce LBP,
- (4) there is a unique “core” group of trunk muscles,
- (5) there is a relationship between stability and back pain.

These assumptions will also be discussed in the therapeutic interventions section further on.

### 3.3.4. Global and Local Stabilizers

In 1989, Bergmark [Ber89] published a mechanical modelling analysis of the stability of the lumbar spine in which a distinction between local and a global system of muscles was made. Local stabilizers were muscles with insertion or origin at the lumbar vertebrae and global stabilizers with origin on the pelvis and insertions on the thoracic cage. In his experiments, Bergmark concluded that force distribution over the local system was independent of the outer load and was only met by different distribution dependent of load in the global system. Therefore he assumed the local system would only perform locally determined actions such as posture control.

The rectus abdominis, external oblique, thoracic erector spinae, longissimus thoracis, iliocostalis lumborum, quadratus lumborum, and internal oblique muscles would be considered global muscles with the functions of large trunk movements and general trunk stability. In low-load situations, the local muscle systems, like the multifidus and transversus abdominis, are associated with intra-abdominal pressure and relaxed inspiration and control the position of the pelvis on the hips and lordosis. In a high-load situation, both systems would interact for extra spinal stability [JP07].

This is the theoretical basis for most lumbar or core stabilization programs: trying to activate the local systems and therefore effectively reducing LBP through dynamic stabilization.

### 3.3.5. Exercise Therapy and Biofeedback Training

Exercise therapy is the most commonly used conservative treatment for LBP and has been proven to be effective both at decreasing pain and improving function in chronic LBP patients and to a certain degree in subacute LBP patients.

Generally speaking, there are two different exercise therapy options. First, general exercise that aims to strengthen all trunk extensors and flexors and second, a stabilization exercise that aims to stabilize more specific muscles. There are no systematic reviews that the author is aware of, directly comparing the effects of general and specific exercise for treating LBP. However, comparisons of stabilization exercises versus manual therapy in a recent review showed stabilization exercise to be in part superior [MJ08].

Additional benefit could also be achieved from the use of biofeedback training in combination with specific stabilization exercises. Biofeedback has already been used for the last five decades with the aim to make normal movement patterns after injury possible.

D8 3 1 Piloting Validation II Hospital.docx	Document Version: 1.0	Date: 2016-03-31	Status: For Approval	Page: 19 / 34
http://www.alfred.eu/		Copyright © ALFRED Project Consortium. All Rights Reserved. Grant Agreement No.: 611218		

Biological information is presented to patients, which would otherwise be unknown, also called augmented or extrinsic feedback, since it goes beyond the available information of the intrinsic (sensory) system. There are two basic principles of biofeedback: direct and transformed feedback. Direct feedback presents the measured variable, for example the current heart rate, as a numerical value on a display of some sort. Transformed feedback describes feedback that is modified by the measured variable, i.e. a tactile feedback for heart rate above a set variable [GPC13]. Since it is known that patients with LBP suffer from an impairment of the intrinsic feedback system, there are several areas of application for biofeedback training [Rib11, DBT05, Pan06].

One possibility for the use of biofeedback is the use of the Wii Balance Board (Nintendo, Kyoto, Japan). It contains four transducers to assess force distribution on the board and the resulting movements in the center of pressure. It was designed as a video game controller in combination with a video game console and its associated software. Instant feedback is also possible and positively affects motivation. However, there are currently no studies which examine the effect of specific stabilizing exercises for LBP in combination with biofeedback devices.

D8 3 1 Piloting Validation II Hospital.docx	Document Version: 1.0	Date: 2016-03-31	Status: For Approval	Page: 20 / 34
http://www.alfred.eu/	Copyright © ALFRED Project Consortium. All Rights Reserved. Grant Agreement No.: 611218			

## 4. Conclusion

Based on the findings of this literature research, a specific exercise regime was developed to explicitly improve the clinical stability of the lower back. The exercises are designed to strengthen the lumbar multifidus muscles which are the major contributor to lumbar stability. The exercises which will be used are so called “bridging exercises”. These exercises are executed while the users are lying on their backs, hips flexed at a 45 degree angle and knees at a 90 degree angle. From this position, the user has to lift her pelvis off the ground such that lower back, pelvis and thigh form a straight line. This position has to be actively held by the user for a period of 20 seconds, before the pelvis can be lowered again in a steady and controlled manner to the initial position (Figure 4).

As previously mentioned, bridging exercises are able to produce high activities of the stabilizing muscles of the spine, especially if they are combined with motions of the extremities of the user (Figure 5). In addition to the benefits of bridging exercises, biofeedback training for the lower back could help to address the localized muscles mass reduction in persons with LBP and therefore reduce the currently high recurrence rates of LBP. Additionally to the benefit of bridging exercises to the lumbar spine, the ALFRED Back Trainer application can provide users with biofeedback information which is displayed to the user on a regular, commercially available tablet computer mounted to a tripod. The main difference of the ALFRED Back Trainer and standard bridging exercises is that the user will additionally lie on two Nintendo Wii balance boards. The balance boards will be horizontally placed under the shoulders and the feet of the user and give feedback of the motion of the user during the bridging exercise (Figure 10). The stabilizing muscles of the spine are by nature very small in size and are not able to produce large motions. For this reason it is very hard to see for the human eye whether or not the local stabilizing muscles are activated equally strong at both sides of the spine during the bridging exercise. Symmetrical activation of the local spinal stabilizers however is necessary to restore the muscle balance in the lower back area in order to reduce the recurrence rates of LBP, increase spinal stability and therefore reduce LBP.

One possibility to visualize symmetric activation of the local spinal muscles during bridging exercises is the use of biofeedback. As previously stated, bridging exercises have shown to be excellent exercises to strengthen the local stabilizers of the spine. However, in order to be able to judge if the user is able to maintain symmetrical activation of the local spinal stabilizing muscles, specific feedback devices could be employed. Optimal symmetrical activity of the stabilizing muscles of the spine during bridging exercises would be achieved, if both feet as well as the shoulders are loaded with an equal amount of bodyweight in all 2-D dimensions. For example, a decreased activation of the stabilizing musculature on the left side would change the kinematics of the lower back and therefore increase the load on the foot or shoulder area during bridging exercises on the left side. With the help of Nintendo Wii balance boards and a tablet, this shift in weight can be made visible to the users during motion. Symmetrical loading of the shoulders and feet is displayed by a ball in a circle. The ball represents the user’s center of mass over the balance board - the closer the ball is to the actual center of the circle, the more equal is the weight distribution of the shoulders and feet (Figure 11). In essence, this is the principle of the ALFRED Back Trainer serious game.

D8 3 1 Piloting Validation II Hospital.docx	Document Version: 1.0	Date: 2016-03-31	Status: For Approval	Page: 21 / 34
http://www.alfred.eu/	Copyright © ALFRED Project Consortium. All Rights Reserved. Grant Agreement No.: 611218			

The users are encouraged to maintain their body position during the exercises as symmetrically as possible. Since a symmetric body position also equals a symmetric activation of the lumbar stabilizing muscles, the hypotheses of the ALFRED Back Trainer is that it can restore spinal stability more effectively as conventional bridging exercises and therefore is superior in the reduction and prevention of LBP.

Figure 4: Starting Position

Figure 5: Arms Opened

Figure 6: Right Arm Lifted

Figure 7: Forefoot Lifted and Arms Opened

Figure 8: Left Forefoot Lifted and Left Arm 45°- angled

## 5. Pilot 2: Procedure

This section will describe the goal of the pilot, applicable regulations, examinations measures, recruitment strategy, pretest procedures, procedure of the main pilot, predicted therapeutically benefits for the users and for future diseased person groups, potential risks and risk management, exit criteria, inclusion/exclusion criteria, documentation details and data protection.

Overall, 60 users will be randomized into three different groups to the pilot. The first group “conventional back training” (CB, 20 users) will receive stabilizing exercises for the lower back, according to the principles from the literature discussed in Chapter 2 and 3 of this document. The second group (CBB, 20 users) will perform identical exercises as the CB group, but with the additional perceived benefit of biofeedback training. Biofeedback will allow the users to visually observe their motions during the exercises on a commercially available tablet PC which will be mounted to a tripod. While the users are lying on two commercially available Nintendo Wii Balance Boards (one underneath their shoulders and one underneath their feet), they can see their body motions during the exercises on the tablet screen. The hypothesis of the pilot is that the additional use of biofeedback during stabilizing exercises for the lower back will lead to increased LBP reduction, higher functionality during activities of daily life, increased muscle strength and improved sleep quality. The third group (C, 20 users) will serve as the control group and will not perform any exercises at all.

[figure not shown]

Figure 9: Back Training with Biofeedback

D8 3 1 Piloting Validation II Hospital.docx	Document Version: 1.0	Date: 2016-03-31	Status: For Approval	Page: 24 / 34
http://www.alfred.eu/	Copyright © ALFRED Project Consortium. All Rights Reserved. Grant Agreement No.: 611218			

Figure 10: Position of the Balance Boards

[figure not shown]

Figure 11: Screenshot of the 'Two Circles' Biofeedback

## 5.1. Aim of the Pilot

The aim of the pilot is the evaluation of exercises meant to strengthen the trunk musculature and reduce or prevent LBP.

Primary goal:

- Find out to what extent physical factors are influenced by a preventive training of the trunk musculature.

Secondary goals:

- Analysis of factors which improve or hinder older adults' participation in preventive training the trunk musculature.
- Analysis of influences of the exercises on sleeping quality.
- Analysis of gender- and age-determined differences concerning problems caused by low back pain.

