## Executive Summary

This deliverable provides the underlying theoretical, non-technical framework for the ALFRED Back Trainer application. The ALFRED Back Trainer was developed in close collaboration with TUDA and is a biofeedback based serious game which was specifically developed in ALFRED to promote specific stabilizing exercises for the lower back in order to reduce or entirely prevent low back pain. The ALFRED Back Trainer will be evaluated for its effectiveness in pilot 2 of the ALFRED project on a group of 60 older adults over a period of ten weeks.

As a first part, this deliverable provides a review of the latest findings on low back pain with respect to its origins, a summary of related anatomical structures and current state of the art exercise-based treatment options. It identifies the role and importance of the most relevant muscles which are needed to adequately stabilize the lower back region in order to reduce or prevent low back pain. It explains the importance of specific exercises for spinal stability in order to prevent or reduce low back pain and the possible advantages of biofeedback training for the treatment of low back pain. Based on these findings a specific exercise regime was developed which aims to restore spinal stability in order to prevent or reduce low back pain. In addition, together with TUDA, the ALFRED Back Trainer was developed. The ALFRED Back Trainer was designed to provide additional muscular stimulus in order to prevent or reduce low back pain and is a result of the review of the current literature and modern serious games technology.

In order to evaluate the benefits of the ALFRED Back Trainer, compared to exercises without the ALFRED Back Trainer, a specific study protocol was developed. The study protocol is the second part of this document. It was developed to explain the procedure of pilot 2 in detail with regards to its specific aim, applicable regulations, recruitment process, overall methodology, risk management and data analysis.

D8 3 1 Piloting Validation II Hospital.docx	Document Version: 1.0	Date: 2016-03-31	Status: For Approval	Page: 4 / 34
http://www.alfred.eu/	Copyright © ALFRED Project Consortium. All Rights Reserved. Grant Agreement No.: 611218			

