## 5.5. Pretest

After the screening process, there will be a pre-test of all involved devices and questionnaires with the older adults in order to ensure an optimal process of the pilot. During the pre-test, users are asked about problems with handling the questionnaire and the instructions and are asked for potential improvements. All comments will be protocolled anonymously by a member of the pilot team.

The critique of the elderly from the pre-test will be taken into consideration and serve as a basis to adapt the questions of the actual pilot in order to warrant maximal comprehensibility.

Changes can contain:

- erasing or reformulating single questions of the questionnaire
- adding choices
- changing words chosen for the instruction
- changing questions of the questionnaire about frame data, healthy behaviour and ratings to improve and estimate the usability
- changes in schedule
- changes in the instructions

D8 3 1 Piloting Validation II Hospital.docx	Document Version: 1.0	Date: 2016-03-31	Status: For Approval	Page: 27 / 34
http://www.alfred.eu/		Copyright © ALFRED Project Consortium. All Rights Reserved. Grant Agreement No.: 611218		

## 5.6. Methodology Pilot 2

At least 24 hours before the actual start of the pilot, the previously screened older adults will receive the participant information, either by Email or via postal service. This information will also contain date and time of the first visit of potential participants of the pilot. At the beginning of the first visit, potential participants will receive the opportunity to clarify any questions relevant to the pilot with the team of the pilot. Once all questions are resolved and the potential participant agrees to enrol in the study, informed consent will be signed and the physical examination will be performed and questionnaires will be filled out by the included subjects.

Each participant receives a unique participant's number by the study personnel. Finally the 60 participants will be randomized either to the group "conventional back training" (CR, 20 participants) or to the group "conventional back training with biofeedback" (CRB, 20 participants), or to the control group (CG, 20 participants).

The following data of the participants will be collected:

- Sociodemographic data to enable clustering the participants (age, sex, educational background)
- Functional questionnaire "Hannover Rücken"
- Oswestry Disability Index

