### Visit 2-25 Intervention group with supervision

The study contains exercises which improve muscular activity and are of medium intensity. The exercises to prevent LBP are conducted on the floor with either a sport mattress (CR) or commercially available Nintendo Wii Balance Boards (CRB) which will provide biofeedback. The exercises will take place in a lying position with the subjects lying on their back. The study wants to examine if the additional employment of biofeedback (CRB) with the same amount of training as in the conventional back training (CR) will lead to different preventive factors of LBP. Furthermore, it shall be examined if the CRB yields additional positive training effects compared to the CR in relation to muscular strength, execution of everyday life activities, balance and LBP. Secondary, it shall be examined if a different acceptance level between the two groups occurs.

The participants of both groups will be trained for a total period of 10 weeks. Users train 2 days a week. Each session takes 40 minutes and consists of a short warmup and 30 minutes of training. The exercises which have to be performed by the subjects are taken

D8 3 1 Piloting Validation II Hospital.docx	Document Version: 1.0	Date: 2016-03-31	Status: For Approval	Page: 28 / 34
http://www.alfred.eu/		Copyright © ALFRED Project Consortium. All Rights Reserved. Grant Agreement No.: 611218		

from the manual of the federal association of German back schools. The training program was compiled by a certified trainer and a physiotherapist. Additionally, in order control the vital signs of the participants, there is a possibility to wear the ALFRED sensor T-shirt which can measure body temperature, breathing rate and heart rate. The biofeedback data of the CRB group are presented to the participants on commercially available Samsung Galaxy Tab 2 Tablet, which is mounted on a tripod. The control group will receive the results of their health assessments by mail, after the end of the study.

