### 5.6.5. Data Analysis

All paper-based questionnaires and physical assessments will be analyzed with Excel and SPSS. The results of the pilot will be presented in the upcoming deliverable D8.3.2.

D8 3 1 Piloting Validation II Hospital.docx	Document Version: 1.0	Date: 2016-03-31	Status: For Approval	Page: 30 / 34
http://www.alfred.eu/		Copyright © ALFRED Project Consortium. All Rights Reserved. Grant Agreement No.: 611218		

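### The goals in Section 5.1 leave out the biofeedback comparison that the pilot is meant to test, and no primary outcome or contrast is named

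*Combined protocol and SAP*

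**What the plan says.** **Goals.** Section 5.1 opens by saying that the pilot evaluates exercises meant to strengthen the trunk and to reduce or prevent low back pain (LBP). Its single primary goal is to "Find out to what extent physical factors are influenced by a preventive training of the trunk musculature". The secondary goals are factors that help or hinder participation, the influence of the exercises on sleep, and gender and age differences. No goal names biofeedback, a comparator, an outcome measure or a time point.

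**Purpose and hypothesis elsewhere.**
- The Executive Summary introduces the study protocol with "In order to evaluate the benefits of the ALFRED Back Trainer, compared to exercises without the ALFRED Back Trainer".
- Section 4 claims superiority over conventional bridging exercises in reducing and preventing LBP.
- Section 5 states as the pilot's hypothesis that "the additional use of biofeedback during stabilizing exercises for the lower back will lead to increased LBP reduction", and adds better daily function, muscle strength and sleep.
- The Visit 2-25 text in Section 5.6 says: "Furthermore, it shall be examined if the CRB yields additional positive training effects compared to the CR in relation to muscular strength". It goes on to everyday activities, balance and LBP.

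**Design and analysis.** "Overall, 60 users will be randomized into three different groups to the pilot", with 20 in each. The arms are conventional training (CB or CR), the same training with biofeedback (CBB or CRB) and a control group without exercise. The final-visit list has ten unranked items. The whole of the analysis method in Section 5.6.5 is: "All paper-based questionnaires and physical assessments will be analyzed with Excel and SPSS".

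**The concern.** The goals and the hypothesis ask different questions. Section 5.1 asks what training does; the other four places ask what biofeedback adds to training. A report that follows Section 5.1 could answer the primary goal from exercise against no exercise and say nothing about the device. Contrasts with the control group cannot stand in for the missing one. The control group does no exercises and has no training visits, so those contrasts combine exercise, supervised contact and, for CRB, biofeedback. Only CRB against CR isolates the Back Trainer.

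The second part follows from the first. With no primary outcome, contrast, significance level or multiplicity rule, the authors can decide after seeing the data which of several dozen comparisons represents the pilot's result. At stake is whether a favourable finding in the results deliverable could be taken as evidence for the Back Trainer.

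**Working it through.** **1. Goals against hypothesis.**

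| Place | Comparison | Effects named |
|---|---|---|
| 5.1 primary goal | none stated | physical factors |
| 5.1 secondary goals | none stated | participation, sleep, gender and age differences |
| Executive Summary | with against without Back Trainer | benefits in general |
| Section 4 | Back Trainer against conventional bridging | spinal stability, LBP |
| Section 5 | biofeedback added to exercise | LBP, function, strength, sleep |
| 5.6, Visit 2-25 | CRB against CR | strength, everyday activities, balance, LBP |

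The biofeedback comparison appears in four places and in none of the goals. The last two rows also differ: Section 5 has sleep and no balance, Visit 2-25 has balance and no sleep, and the order is not the same.

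**2. How many tests are open.** The Visit 26 list has 10 items. Endurance covers three muscle groups, which gives 10 + 2 = 12. Counting Schober and Ott as two values (an assumption) gives 13. Leaving out the health-behaviour questions, whose number is not stated, gives 12 again. Three arms give three pairwise contrasts, so 12 × 3 = 36 tests (30 to 39 for 10 to 13 outcomes). Gender and age analyses and within-group changes are not counted.

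**3. False-positive risk.** The plan states no error rate, so there is no figure to reproduce. Assumptions: two-sided 5% per test, no adjustment, 20 per arm, normal outcomes with equal correlation, no true effect.

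If all 36 tests were independent: 1 − 0.95^36 = 84%. They are not, because contrasts share arms, so the chance was simulated with pairwise t-tests (repeat runs agree to about one percentage point). For 12 outcomes:

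| Correlation | Any difference, 3 contrasts | Benefit, 3 contrasts | Any difference, CRB vs CR | Benefit, CRB vs CR |
|---|---|---|---|---|
| 0 | 79% | 56% | 46% | 26% |
| 0.2 | 76% | 49% | 43% | 22% |
| 0.3 | 72% | 45% | 40% | 20% |
| 0.5 | 61% | 37% | 32% | 16% |
| 0.7 | 48% | 28% | 24% | 12% |

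Benefit means significant in the favourable direction: CR over control, CRB over control, or CRB over CR. The CRB-CR entries at correlation 0 can be checked directly: 1 − 0.95^12 = 46% and 1 − 0.975^12 = 26%. With 10 or 13 outcomes at correlation 0, the three-contrast benefit figure is about 50% or 58%.

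The three-contrast columns need no true effect anywhere. The CRB-CR columns need only that biofeedback adds nothing, so they still apply if exercise itself works.

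If each outcome were tested pairwise only after a significant three-group analysis of variance, any false-positive difference falls to 47% (correlation 0) or 32% (0.5), and a false benefit to 30% or 20%. One prespecified two-sided 5% test carries 5% for any difference and 2.5% for a false benefit.

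**4. What one primary test can detect.** With 20 against 20, the difference detectable with 80% power is (1.96 + 0.84) × √(2/20) = 0.89 SD, or 0.91 SD with the t distribution. Power at assumed true effects of 0.3, 0.5 and 0.8 SD is 15%, 34% and 69%. Bonferroni over 36 tests (0.05/36 = 0.0014) would need about 1.3 SD or more.

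**The case against.** The biofeedback comparison is not absent from the plan: the Visit 2-25 text says it will be examined. That is right, and the defect is a mismatch between goals and methods. It is also true that Section 5.1's opening sentence mentions LBP, that sleep is ranked as secondary there, and that the no-exercise arm answers the training question the section poses. That question deserves to stay as a stated goal.

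A reader might infer from the number of open tests that a false claim of benefit is more likely than not. The documents do not support that. They state no significance level and do not say that all 36 tests will be run. Even if they are, a false benefit exceeds 50% only when the outcomes are almost uncorrelated. Two back-function questionnaires, a pain scale and physical tests in the same people are unlikely to be so. On CRB against CR the chance is well below 50% throughout. What does exceed 50%, up to a correlation of about 0.65, is the chance of some false-positive difference in either direction.

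Section 5.3 calls this a pilot study, and a pilot need not control error strictly. That stands in part: labelling everything exploratory would be a coherent alternative. But the plan does not do so. It states a superiority hypothesis, and the Executive Summary says the trainer will be evaluated for its effectiveness.

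A full testing sequence across pain, function, strength and sleep would go further than the text supports. Sections 5 and 5.6 list the domains in different orders, Section 5.1 makes sleep secondary, and nothing favours one function questionnaire or one endurance test over another.

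**Conclusion.** The concern holds. Section 5.1's goals omit the comparison that the rest of the document gives as the reason for the pilot, and Section 5.6.5 does not name a primary outcome or contrast that would repair it. This can be read directly from the text and rests on no assumption.

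The error rates show the size of the consequence and are conditional. If 12 outcomes are tested on three contrasts, unadjusted at two-sided 5% with no true effect, the chance of at least one false-positive difference is about 61% to 79%, and of a false benefit about 37% to 56% (correlation 0.5 to 0). On CRB against CR alone, a false benefit has a chance of about 16% to 26%, roughly six to ten times the 2.5% of a single prespecified test.

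**What to change.** In Sections 5.1 and 5.6.5:
- State CRB against CR at Visit 26, on one outcome named in advance, as the primary comparison, with its test and significance level. The back-pain VAS is the natural choice: LBP reduction comes first in the Section 5 hypothesis and is part of the superiority claim in Section 4. The sponsor may prefer another outcome; what matters is naming one.
- Keep the effect of training (CR and CRB, each against control) as a separate stated goal.
- Report that goal and all other outcomes, including function, strength, balance and sleep, with 95% confidence intervals, labelled exploratory.
- Reconcile the domain lists in Section 5 and the Visit 2-25 text.
- A fixed testing sequence after the first outcome is optional.

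Settle this once the pretest changes to the questionnaires are final, and before any Visit 26 data are seen. The document is still marked for approval and the final ethics vote was pending, so there is room to do it.

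**Cost.** No extra participants or measurements: the VAS is already taken at the first and final visits. The price is in what can be claimed. With 20 per arm the primary test has 80% power only for about 0.9 SD, and about 34% for 0.5 SD, so a null result would be inconclusive and should be reported as such. A favourable result on any other outcome could no longer be presented as proof of effectiveness.
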